- (3) Group 3 followed the standard weight loss program enhanced by personalized feedback by a nutritionist based on lifestyle habits reported in the platform for 12 weeks and the standard weight loss program for the following 12 weeks.

Subsequently, subjects received an automatic email with detailed information on the groups they were allocated to. Researchers were blinded to participants' allocation.

Outcome measures

All outcomes will be assessed at baseline, 12 and 24 weeks afterwards. Weight and BMI change are the primary outcomes of the study and will be self-reported by the participants. Secondary outcomes will be changes in dietary habits, food-related behaviors, physical activity habits, sedentary behaviors, quality of life, health perception, online activity and users' satisfaction, as detailed in Table 2. Outcome assessors will be blinded to group allocation.

Sample size

Based on a 90% power to detect a significant difference of 4kg weight loss between groups, assuming the SD of weight is 6.0 and using a two-sided significance level of 0.05, and a 40% attrition rate, a sample size of 90 participants was calculated for each group.

Interventions

The interventions will be delivered online for 24 weeks, with new program content distributed to the user weekly for Groups 2 and 3. The content of dietary and physical activity recommendations was based on Brazilian and international evidence-based guidelines. Dietary recommendations focused on particular Brazilian habits. Physical activity recommendations focused on increasing time of leisure exercise and decreasing sitting time.

In group 1, subjects have access to four videos with information on health consequences of excessive weight, dietary and physical activity weight loss recommendations, as well as strategies to behavior change. They also received an e-book with lifestyle habits and behavioral recommendations to lose weight. Access to the study website will be limited for the first 24 weeks and they have been asked not to undertake any other weight-loss program during this time. They will be invited to report their weight, dietary and physical activity habits at 12 and 24 weeks after baseline by email. Afterwards, they will gain access to the standard online platform.

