Group 2 has access to the study website program for 24 weeks. The platform used in this study was adapted from a commercial product (Cybergia® Inc.), which runs various Internet-based health programs in Brazil (www.cybergia.com). The platform is cloud-based progressive, web-app developed and can be accessed in desktop and smartphone environments. It has three areas: 1) Main area, presenting weekly updated tasks such as content (video, articles), suggested dietary and physical activities and questionnaires; 2) Self-monitoring area, containing a food diary, functionalities for activity self-report and charts; 3) Social area, containing a private social network where users can share and react to photos and posts. Connecting these areas, the platform presents gamification mechanics, such as weekly points (connected to completing tasks and interacting with other participants) and social challenges, which invite users to complete one-time

specific tasks and share their accomplishments. Interaction with the project's team was restricted to public posts and selected comments on the social network.

Group 3 has access to this online program plus weekly individual chat in the platform with a dietitian. At these times, they have the opportunity to discuss and manage individual issues.

Quality Control

Several procedures will be employed to optimize the quality of the study and maximize internal validity and reliability of the program delivery and outcome assessments. Assessors of the main outcome measures are blinded to the participants' group allocation. Assessment protocols and orientations to participants were standardized in written documents. Validation of self-reported weight and height will be performed by correlation to measurements for a random sample of 10% of the study population. Personnel will be trained on anthropometry procedures prior to the assessment. Regular team meetings between the clinical and information technology teams, in order to align strategies, are planned.

Measurements and instruments

Demographic Data

Data on gender, education, civil status and place of work will be collected at baseline. Questionnaires to obtain current medical conditions and medications will be completed at baseline and 24 weeks.

Anthropometry

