Weight and height will be self-reported by the participants and BMI will be calculated by the formula weight in kg/ (height*height) in m². For the random 10% sample selected for additional measurements, weight will be measured in light clothing, without shoes on a Welmy ® analogic scale with stadiometer. For this sample, waist circumference will be measured at the mid-level between the last rib and the iliac crest using an inelastic tape and body composition will be measured by electrical bioimpedance using Sanny ® Bioimpedance.

Dietary intake and food-related behavior

For groups 2 and 3, calculation of the total daily caloric intake and dietary nutrients will be performed by an automatic dietary calculator which was based on food nutrition composition tables for the Brazilian population (<http://www.unicamp.br/nepa/taco/>).

Questions about the total number of daily serves of fruit and vegetables, and whole carbohydrates sources, as well as weekly serves of sweetened beverages and snack foods will be applied. Moreover, food-related behaviors, including number of days taking breakfast, number of daily meals, frequency of take-away food consumption and eating while watching television will be assessed by questionnaires.

Eating behavior

The random sample selected to anthropometry will have cognitive and behavioral components of eating assessed across three scales of cognitive restraint, uncontrolled eating and emotional eating by the Brazilian version of the Three Factor Eating Questionnaire-R21, (TFEQ-R21).

Physical activity and sedentary behavior

- The short-form of the International Physical Activity Questionnaire (IPAQ) will be used to estimate total MET-minutes/week and to classify participants into either high, medium or low physical activity categories according to the IPAQ Scoring Protocol [18].
- The daily screen-time (i.e., in front of TV, computers, video games, smartphones) and the daily sitting time will be used to assess sedentary behavior.
- Pedometers: the number of steps will be measured by XXX pedometer in the sample randomly selected to anthropometry.

Health perception

The Brazilian version of the *12-item Short-Form Health Survey – Version 2*, (QualityMetric Incorporated, Lincoln, RI, USA) which is a self-reported measure of health-related quality of life (HRQoL) designed to investigate multidimensional aspects

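### Staff blinding does not protect the primary outcome, because weight and BMI are reported by participants who know their arm, and the plan's one check on self-report is not set up to detect a difference between arms.

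*Protocol*

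**What the plan says.** On who supplies the primary outcome, the Outcome measures section of the protocol says "Weight and BMI change are the primary outcomes of the study and will be self-reported by the participants". The Anthropometry section confirms it: "Weight and height will be self-reported by the participants", with BMI calculated from the two.

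On who knows the allocation, the Randomization and allocation section says that after randomization "subjects received an automatic email with detailed information on the groups they were allocated to". It adds "Researchers were blinded to participants' allocation".

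On blinded assessment, Outcome measures says "Outcome assessors will be blinded to group allocation". Quality Control repeats this for the main outcomes, "Assessors of the main outcome measures are blinded", among the procedures meant to support internal validity.

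On checking self-report, Quality Control plans to validate reported weight and height by correlating them with measured values in a random tenth of participants. It gives no time point, no comparison between arms and no criterion for acceptable agreement.

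On analysis, the SAP specifies a linear model for weight with treatment group and baseline weight, plus other baseline covariates. Hochberg's procedure is applied at 2.5% per time point. The SAP uses neither the validation data nor any analysis that allows for reporting error.

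**The concern.** Blinding an assessor protects an outcome when the assessor's judgement or measurement produces the value. Here the participant produces it, after being told the arm, and the documents describe no staff member who assesses the primary weight. The blinding statement in Quality Control names the main outcome measures, so it cannot be read as covering only the measured subsample.

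If participants in one arm come to shade their reported weight more than those in another, the shift goes straight into the estimated group difference. A trial report that repeats the protocol's blinding statement would credit the primary outcome with a protection against detection bias that it lacks. The questionnaire outcomes (diet, activity, quality of life, body image) are in the same position.

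**Working it through.** The point rests on the text. The arithmetic only shows what an assumed shift would do.

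**1. What staff blinding can reach**

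| Outcome | Who produces the value | Does that person know the arm? |
|---|---|---|
| Primary weight and BMI | Participant | Yes, by email |
| Questionnaires | Participant | Yes, by email |
| On-site measurements, 10% subsample | Trained staff | Stated as blinded |

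Staff blinding can bear on the third row and on data handling. It cannot bear on the first two.

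**2. What baseline adjustment can reach.** Randomization was stratified by BMI category, so weight and height were reported before the allocation email. If that weight is the model's baseline, a constant personal habit of under-reporting is present at baseline and follow-up and is balanced by randomization. If the habit changes by b kg after allocation in one arm only, that arm's contrast moves by b kg and the adjustment does not remove it.

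**3. What the correlation can reach.** The documents give no reporting-error figures. Assume a between-person weight SD of 15 kg, a reporting-error SD of 2 kg, and under-reporting of b kg in both active arms (two thirds of the sample).

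- Variance of reported weight = 15² + 2² + b² × (2/3)(1/3).
- b = 0: correlation = 15/√229 = 0.991.
- b = 2: correlation = 15/√(229 + 0.889) = 0.989.

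A 2 kg shift, half the 4 kg target difference, changes the correlation by 0.002.

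**4. What an assumed shift would do to the primary test**

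The Sample size section gives SD 6.0 kg, 90 per group and 40% attrition, so completers = 90 × 0.6 = 54 per arm. (Its other inputs, 4 kg, 90% power and two-sided 5%, give 48 per group, or 48/0.6 = 80, rather than 90. That is a separate matter, on the conservative side.)

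SE of a contrast = 6 × √(2/54) = 1.155 kg.

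The SAP does not list the contrasts in the Hochberg family. I assume two, each active group against Group 1, with two-sided tests at one time point. Hochberg then rejects a contrast if its p-value is at most 0.0125, or if both p-values are at most 0.025. With no true effect and extra under-reporting b in one active arm:

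- First route, critical value 2.498: P = 1 − Φ(2.498 − b/1.155) + Φ(−2.498 − b/1.155).
- The second route adds 0.1 to 0.2 percentage points (simulation with the shared control arm).

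| Assumed b | First route | Full Hochberg | Single unadjusted test at 2.5% |
|---|---|---|---|
| 0 kg | 1.25% | 1.4% | 2.5% |
| 0.5 kg | 2.1% | 2.3% | 3.9% |
| 1 kg | 5.2% | 5.3% | 8.5% |
| 2 kg | 22.2% | 22.3% | 30.5% |

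The last column is shown only because it is the simpler calculation. It overstates the risk under the SAP's own rule. If baseline adjustment brings the residual SD below 6.0 kg, the rates for a given b rise.

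**5. What a by-arm comparison in the subsample could show.** With 270 enrolled, 10% is 27 people, 9 per arm if evenly spread, or about 5 after 40% attrition (9 × 0.6 = 5.4). For an assumed error SD s, the 95% half-width for the between-arm difference in mean error is t × s × √(2/k):

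- k = 9: 2.120 × s × 0.471, or 1.0 kg (s = 1) to 3.0 kg (s = 3).
- k = 5: 2.306 × s × 0.632, or 1.5 kg (s = 1) to 4.4 kg (s = 3).

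**The case against.** Self-report is a legitimate choice for an online trial. The protocol states it openly, along with the allocation email, so a careful reader can see the true position. Quality Control treats staff and participants separately, and blinded staff still have a role in data handling and the measured subsample. The plan includes a validation exercise, and its baseline term deals with habitual under-reporting. All of this stands, and it limits the point to differential reporting after allocation.

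A reader might go further and infer that any bias must favour the intervention, because Groups 2 and 3 earn points and share accomplishments and Group 3 has contact with a dietitian. The documents do not support that:

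- Points are tied to completing tasks and interacting with others, not to weight.
- Group 1 also intended to lose weight and received weight-loss material.
- Group 3's personalised feedback is limited to the first 12 weeks.
- More self-monitoring could make reports more accurate.

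A reader might also infer that blinding is absent altogether, or that the results are biased. The first overlooks the measured subsample. The second cannot be drawn from documents that contain no results.

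The validation exercise does not answer the remaining point. As specified, it is a pooled correlation on about 27 people with no link to the primary analysis.

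**Conclusion.** The point holds in this limited form. The two assessor-blinding statements credit the main outcomes with a protection that cannot apply to participant-reported weight and BMI. Neither the baseline adjustment nor the planned correlation covers a reporting change after allocation that differs by arm.

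Whether such a change occurs, in which direction and by how much, is unknown. The false-positive rates of about 2%, 5% and 22% are illustrations. They rest on assumed shifts of 0.5, 1 and 2 kg, SD 6.0 kg, 54 completers per arm, no true effect and a two-contrast Hochberg family. On those assumptions a 0.5 kg shift does little (1.4% with no shift, 2.3% with it), while a 2 kg shift matters. The wording should be corrected and the validation made informative by arm. Nothing here calls for replacing self-report.

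**What to change.** 1. In Outcome measures and in Quality Control, replace the assessor-blinding sentences with, for example: *Primary and questionnaire outcomes are reported by participants who know their allocation. Staff blinding applies only to data handling and to the on-site measurements in the 10% subsample.*

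2. In the SAP, do not rely on the pooled correlation alone. Report the mean of reported minus measured weight with limits of agreement, by arm, at each time point where the subsample is measured, and state those time points. Read the primary contrast's confidence interval against the between-arm difference in reporting error. If the subsample is measured only at baseline, say that the check cannot address reporting at 12 or 24 weeks.

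A sensitivity analysis that adds a constant to one arm's weights would contribute little. In this linear model it moves the contrast by that constant and leaves the SE unchanged, so the shift at which significance is lost is simply the confidence limit nearest zero. The documents also offer no basis for choosing a threshold.

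The cost is two sentences and one small table from measurements already planned. The stated risk of bias becomes less favourable, and the by-arm estimate will be too imprecise to rule out a shift of a kilogram or more.

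### Self-reported weight and height are validated only by correlation, which cannot show the direction or size of a reporting error; signed differences with limits of agreement should replace it (minor)

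*Protocol*

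**What the plan says.** In Outcome measures, the Protocol states: "Weight and BMI change are the primary outcomes of the study and will be self-reported by the participants". Under Randomization and allocation, participants learn their group: "subjects received an automatic email with detailed information on the groups they were allocated to". Blinding is described for assessors, in Outcome measures ("Outcome assessors will be blinded to group allocation") and again in Quality Control ("Assessors of the main outcome measures are blinded").

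The validation is one sentence in Quality Control: "Validation of self-reported weight and height will be performed by correlation to measurements for a random sample of 10% of the study population". The Anthropometry section describes the reference measurement: "For the random 10% sample selected for additional measurements, weight will be measured in light clothing, without shoes". Paired self-reported and measured values are therefore already planned.

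The type of correlation is not named. No mean difference, limits of agreement or threshold for acceptable agreement is given, and the SAP does not mention the validation. The weighing visits of the sample are not stated separately. The general statement "All outcomes will be assessed at baseline, 12 and 24 weeks afterwards" may cover them, and the Table 2 to which the section refers is not visible in the text available. Timing is not treated as a defect here.

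**The concern.** The person who supplies the primary measurement knows the allocation, so blinding the assessors does not protect the report itself. That leaves the 10% sample as the only stated check on the reported values, and Quality Control lists it among the procedures meant to support internal validity.

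Correlation measures how closely two sets of values follow a straight line. It does not measure whether they agree. A group that under-reports by several kilograms can still give r close to 1. At stake is the conclusion drawn from the substudy: a high r could be reported as reassurance about bias that it cannot give.

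**Working it through.** The documents give no numerical result or target for the validation, so there is no figure of the plan's own to reproduce.

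**Inputs from the Protocol.** A 10% sample; 90 per group in three groups; 40% attrition (Sample size). Taking 3 x 90 = 270 as enrolment (an assumption, since actual enrolment is not given), the sample is 27, or 9 per arm. After attrition it is 9 x 0.6 = 5.4, about 5 per arm.

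**Assumed inputs.** SD of true weight (SDw) 12 kg, with 6 kg as an alternative because the Sample size section uses 6.0. SD of random reporting error (SDe) 1 to 3 kg. Pearson's r unless stated.

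**1. Uniform misreport.** Let reported = true + a + random error. Then r = SDw / sqrt(SDw² + SDe²). The shift a does not appear. For SDw 12 and SDe 2, r = 12 / sqrt(144 + 4) = 0.986 whether a is 0, 2 or 4 kg.

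**2. Misreport of d kg in one of three equal arms.** The shift adds variance (1/3)(2/3)d² = (2/9)d², so r = SDw / sqrt(SDw² + SDe² + (2/9)d²).

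| SDw, SDe | d = 0 | d = 2 | d = 4 |
|---|---|---|---|
| 12, 1 | 0.997 | 0.994 | 0.985 |
| 12, 2 | 0.986 | 0.983 | 0.975 |
| 12, 3 | 0.970 | 0.967 | 0.959 |
| 6, 1 | 0.986 | 0.975 | 0.942 |

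The term (2/9)d² enters exactly as extra random-error variance would. The largest fall, to 0.942, is also what no bias with error SD sqrt(1 + (2/9) x 16) = 2.13 kg would give. This lack of specificity holds for every choice of SDs.

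**3. How visible the fall is with 27 people (simulation).** For SDw 12 and SDe 2, the 95% range of r is 0.971 to 0.994 with no shift and 0.965 to 0.993 with 2 kg in one arm, an almost complete overlap. For SDe 1 and a 4 kg shift the ranges separate. At SDw 12 the unshifted range starts at 0.993 and the shifted range ends at 0.992; at SDw 6 the corresponding values are 0.971 and 0.969.

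**4. A concordance coefficient instead.** Concordance = 2SDw² / (2SDw² + SDe² + V + M²), where V is the variance added by the shift and M the mean shift. For SDw 12, SDe 2 and 2 kg:
- no shift: 288/292 = 0.986
- uniform (V = 0, M = 2): 288/296 = 0.973
- one arm (V = 8/9, M = 2/3): 288/293.33 = 0.982

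It reacts to a uniform shift, but gives neither direction nor kilograms and still mixes bias with random error.

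**5. Mean signed difference (self-reported minus measured).** The 95% half-width is t x SDe / sqrt(27) with t = 2.056 on 26 df: 0.40, 0.79 and 1.19 kg for SDe 1, 2 and 3. Under a uniform 2 kg misreport the CI excludes zero in over 99%, over 99% and 92% of samples. Under 2 kg in one arm the overall mean shift is only 2/3 kg, and the CI excludes zero in about 72%, 31% and 17% (simulation with 9 per arm).

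**6. By-arm results.** The half-width for a between-arm difference in mean error is t x SDe x sqrt(2/n). With n = 9 (16 df, t = 2.120) this is 1.0, 2.0 and 3.0 kg; with n = 5 (8 df, t = 2.306) it is 1.5, 2.9 and 4.4 kg. For a by-arm limit of agreement, the approximate half-width t x SDe x sqrt(1/n + 1.96²/(2(n - 1))) on n - 1 df is 1.37 x SDe at n = 9 and 2.29 x SDe at n = 5.

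**7. Effect on the primary contrast.** The SAP regresses weight on group and baseline weight. Additive error common to all arms drops out of the group contrast. Proportional error common to all arms rescales it: a 5% under-report turns a 4 kg difference into 0.95 x 4 = 3.8 kg. Error in one arm after baseline moves it about kilogram for kilogram.

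**The case against.** The strongest objection is that the benefit and the harm belong to different errors. Signed differences do well for a uniform error, yet a uniform additive error cancels in the treatment contrast. The error that would distort the contrast is confined to one arm, and there signed differences do little better: the overall mean cannot identify the arm, and the by-arm comparison is imprecise. This stands, and it limits the weight of the point.

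Three further objections also stand. How far r falls under a one-arm shift depends on the assumed SDs and shift, and in some cases the fall would be visible; only the non-specificity, and the blindness of Pearson's r to a uniform shift, hold throughout. The signed difference does not isolate misreporting. It also contains differences in clothing, scale and timing, because the sample is weighed in light clothing on a study scale while the documents do not say how participants weigh themselves. Limits of agreement by arm would be too imprecise to use.

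A reader might infer that validating by correlation raises the false-positive rate of the primary analysis. It does not. Any such inflation would come from unblinded self-report and would be the same whichever validation statistic was chosen. Nor do the documents show that misreporting differs by arm. Every arm enrolled people who intended to lose weight and received weight-loss material, so some misreporting may be common to all.

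The sentence in Quality Control does not exclude further agreement statistics. But correlation is the only one named, and the SAP names none.

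**Conclusion.** The point holds as a minor one. The stated validation cannot show whether self-reported weight or height is biased, in which direction, or by how much. A high r, or a high concordance coefficient, would not settle it. The invariance of Pearson's r to a uniform shift and its non-specificity to a one-arm shift are algebraic. The numerical sizes rest on assumed SDs and an assumed enrolment of 270.

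The pairs already planned would support a usable estimate of the overall error and only a weak description by arm. Changing the statistic leaves the primary analysis and its exposure to differential misreporting as they were. The documents do not support a stronger reading, that the primary result is biased or that this change would protect it.

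**What to change.** In Quality Control, replace the correlation with the overall mean signed difference (self-reported minus measured), its 95% CI and limits of agreement, for both weight and height, at each visit at which the sample is weighed. State that the difference also reflects clothing, scale and timing.

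If the sample is weighed after allocation, add the mean signed difference with CI by randomised group, labelled as descriptive and without by-arm limits of agreement. If weighing takes place only at baseline, omit the by-arm table: self-reports then probably precede allocation, since randomisation is stratified by BMI category, and any difference would be chance.

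Do not present a high correlation or assessor blinding as protection against self-report bias. State that differential misreporting after allocation remains largely unassessed, or wholly unassessed if the sample is weighed only at baseline.

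The cost is a change of wording and a short descriptive analysis, with no new measurement. The drawback is that the by-arm figures may be inconclusive and must be reported as such.
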